### 5. Amendments

Table 1: Amendmen	ts and updates
-------------------	----------------

Amendment number	Reason for amendment	New version number	Effective date
AM01	• Inclusion of change in UACR endpoint (time to 30% decline) as a secondary outcome, with potential consideration of other threshold values	v 2.0	03 JUL 2024
	• Clarification that the secondary analyses of individual components of the primary composite outcome will be performed in the same analysis set as the primary composite outcome		
	• Clarification that secondary subgroup analyses and secondary treatment strategy analyses may be performed for outcomes other than the primary compositive cardiovascular outcome		
	• Removal of new-onset atrial fibrillation as an exploratory outcome		
	• Inclusion of change in UACR over time at 4 months and 12 months as exploratory outcomes		
	
 
Change of data source to HealthVerity® Chronic Kidney Disease Masterset and associated changes to the Representativeness, Study Size, Data Management, Quality Control, and Protection of Human Subjects sections
 
		

 $\overline{AM}$  = amendment; UACR = urine albumin-creatine ratio.

## 6. Milestones

Table 2 presents planned milestones for the project. These milestones are based on timely review and approval of the project. Administrative changes to milestones due to delays in study preparation and enrolment do not require amendments to the protocol. Revised study timelines and milestones that do not constitute a need for a formal protocol amendment are tracked in a stand-alone document (Annex 1).

#### Table 2. Milestones

Milestone	Planned date
PRC approval	14-MAR-2024
Public registration of study protocol	30-JUL-2024
Start of data collection a	01-OCT-2024
Start of data analysis	01-OCT-2024
End of data collection/analysis	30-JUN-2025
Final report of study results	31-DEC-2025

PRC = protocol review committee.

a For secondary use of data, the start of data collection is the date from which data extraction starts.

## 7. Rationale and background

Chronic kidney disease (CKD) is defined as abnormalities of kidney structure or function that are present for more than 3 months and have serious health implications. Patients with CKD have an increased risk of kidney failure, cardiovascular disease, and death. Thus, the treatment goal in CKD is not only to prevent dialysis or transplant but also to reduce the cardiovascular disease burden; this is especially relevant among patients with diabetes [1,2]. Patients with type 2 diabetes (T2D) have a high prevalence and incidence of CKD [3]. The prevalence of CKD among patients with diabetes is 38% in the United States (US) [4].

Disease management strategies for patients with CKD and T2D include treatment of risk factors for CKD (e.g., high blood pressure) with drugs or lifestyle modification [5], with the goal to prevent further loss of kidney function or progression to end-stage kidney failure. Multiple available therapies are indicated for (or commonly used for, though not formally indicated) the prevention and treatment of CKD among patients with T2D in the US, including renin-angiotensin system inhibitor drugs (e.g., angiotensin-converting enzyme inhibitors [ACEi], angiotensin receptor blockers [ARB]), sodium-glucose cotransporter 2 inhibitors (SGLT2i), and finerenone.

Finerenone is an oral, selective non-steroidal mineralocorticoid receptor antagonist (nsMRA) developed by Bayer for the treatment of CKD in patients with T2D. Because of its mechanism of action, finerenone is expected to have a lower risk of inducing hyperkalaemia than spironolactone—a steroidal nonselective mineralocorticoid receptor antagonist (MRA)— which has been shown in clinical studies [6]. In the phase 3, event-driven, placebo-controlled FIDELIO trial [7], results showed that, among patients with stage 3 or 4 CKD with severely elevated albuminuria and T2D, finerenone, when added to standard of care, reduced the incidence of CKD progression [8] and a composite cardiovascular outcome that included time to cardiovascular death, nonfatal myocardial infarction, nonfatal stroke, or hospitalisation for heart failure [9]. In the FIGARO trial [10], patients receiving finerenone had less severe kidney impairment, either stage 2 to 4 CKD and moderately elevated albuminuria, or stage 1 or 2 CKD and severely increased albuminuria, but the cardiovascular benefit seen in the FIDELIO trial extended to those patients with less kidney impairment but who were still at high cardiovascular risk [11]. In the prespecified pooled analysis of the FIDELIO and

FIGARO trials (FIDELITY) [12], the positive effects were demonstrated for both CKD and cardiovascular outcomes across a broad spectrum of CKD [12].

Finerenone received approval from the US Food and Drug Administration (FDA) on 09 July 2021 and is indicated for adult patients with CKD associated with T2D to reduce the risk of sustained estimated glomerular filtration rate (eGFR) decline, kidney failure, cardiovascular death, nonfatal myocardial infarction, and hospitalisation for heart failure [13].

Because patients receiving finerenone in clinical practice may differ from patients who are included in controlled clinical trials, it is important to evaluate the real-world effectiveness and safety of finerenone early after marketing approval as part of routine clinical practice. For example, pivotal trials of finerenone required participants to be on maximally tolerated doses of an ACEi or ARB, and participants needed to meet strict definitions of CKD, including persistent very high albuminuria and eGFR less than 60 [14,15]; however, the US label for finerenone [13] and treatment guidelines [16] allow for broader use of finerenone in less severe kidney disease and without comedication use.

The FIRST-2.5 study is part of the larger research programme conducted within the Finerenone Multidatabase Network Data Generation (FOUNTAIN) research programme. The FIRST-2.5 study is the third study of the FIRST programme, a series of studies conducted in cohorts of patients with CKD and T2D in clinical practice. The goal of the currently ongoing FIRST-1 study is to describe renal and cardiovascular outcomes and healthcare resource utilisation among patients who initiate ACEi/ARB, SGLT2i, glucagon-like peptide-1 receptor agonists (GLP-1 Ras), or steroidal MRA. FIRST-2.0 will describe patients who initiate finerenone in the initial time period after FDA approval in the US and will describe temporal changes in eGFR and urine albumin-creatinine ratio (UACR) and the incidence of short-term clinical outcomes. The current study, FIRST-2.5, will evaluate the effectiveness and safety of finerenone in real-world use by estimating the association of finerenone use with CKD and T2D in the US.

## 8. Research questions and objectives

This study addresses the research question of whether finerenone is effective and safe when used in real-world populations of adult patients in the US with CKD and T2D compared with that in patients with CKD and T2D not using finerenone. The primary treatment strategy evaluated by this study will be initiating treatment with finerenone according to the approved label in the US and not discontinuing treatment, except in the case of hyperkalaemia or end-stage kidney failure (Section 9.3.2.1).

### 8.1. Primary objective

The primary objective in this study is the following:

• To assess the effectiveness of finerenone by estimating the risk of a composite cardiovascular outcome (i.e., first occurrence of fatal or nonfatal acute myocardial infarction or hospitalisation for heart failure) in patients with CKD and T2D initiating finerenone compared with that in patients with CKD and T2D not using finerenone.

### 8.2. Secondary objectives

The secondary objectives in this study are the following:

• To estimate the risk of the individual components of a composite cardiovascular outcome (i.e., first occurrence of fatal or nonfatal acute myocardial infarction; first

occurrence of hospitalisation for heart failure) in patients with CKD and T2D initiating finerenone compared with that in patients with CKD and T2D not using finerenone (in the same primary study cohort as the primary analysis).

- To estimate the risk of new-onset heart failure in patients with CKD and T2D initiating finerenone compared with that in patients with CKD and T2D not using finerenone (in a subset of the primary study cohort from which patients with a history of heart failure are excluded).
- To estimate the risk of a decline in UACR (i.e., first occurrence of specific UACR decline thresholds) in patients with CKD and T2D initiating finerenone compared with that in patients with CKD and T2D not using finerenone (in a subset of the cohort of patients with baseline UACR values).
- To assess the safety of finerenone by estimating the risk of hyperkalaemia in patients with CKD and T2D initiating finerenone compared with that in patients with CKD and T2D not using finerenone.
- To estimate the risk of the above mentioned outcomes in clinically relevant subgroups of patients with CKD and T2D initiating finerenone compared with that in patients with CKD and T2D not using finerenone.
- To assess the effectiveness of initiating finerenone and titrating dosage according to the approved label by estimating the risk of outcomes of interest in patients with CKD and T2D initiating finerenone and uptitrating to 20 mg (when recommended) compared with that in patients with CKD and T2D not using finerenone.

### 8.3. Exploratory objectives

The exploratory objectives in this study are the following:

- To estimate the risk of all-cause mortality in patients with CKD and T2D initiating finerenone compared with that in patients with CKD and T2D not using finerenone.
- To describe the change in UACR over time at 4 months and 12 months in patients with CKD and T2D initiating finerenone and in patients with CKD and T2D not using finerenone (in a subset of the cohort of patients with baseline UACR values).

### 9. **Research methods**

[figure not shown]
#### 9.1. Study design

This is a new user cohort study utilising existing healthcare data of patients with CKD and T2D initiating finerenone compared with patients with CKD and T2D not using finerenone. The cohort design will allow for observation of all person-time since finerenone initiation and will correctly align the evaluation of eligibility criteria with the beginning of follow-up.

Time 0 will be identified for both the exposed and comparator groups (Section 9.2.1.1), and all variable assessment time windows (e.g., washout, covariate assessment, follow-up) will be anchored on Time 0 (Figure 1).

Before the start of the analyses, a statistical analysis plan (SAP) will be prepared to describe the details of the statistical techniques, define concepts, and operationalise all study variables needed for analysis in the data source(s).

#### Figure 1: Study design overview

AMI = acute myocardial infarction; CKD = chronic kidney disease; eGFR = estimated glomerular filtration rate; HCU = healthcare utilisation; K = potassium; SES = socioeconomic status; T1D = type 1 diabetes; T2D = type 2 diabetes

- a Identified with recorded diagnosis of CKD or eGFR measurements.
- b Duration of T2D; amputations of lower limb; duration of CKD; CKD stage.
- c Outcome-specific washout criteria will be applied to create the relevant analysis sets for each outcome.
- d End of the study period; disenrollment from the database; deviation from the treatment strategy (finerenone use or non-use).

#### 9.2. Setting

#### 9.2.1. Study population and selection criteria

The source population for the study will consist of adults with CKD and T2D who are eligible for finerenone prescription after the approval of finerenone in the US. The study cohort will identify patients who initiate finerenone and a comparator group of individuals with CKD and T2D not using finerenone. All eligible adult individuals (aged  $\geq$  18 years) in the data source will be selected for the study cohort without sampling from the source population. There will be no restrictions of the study population based on sex, race, or ethnicity.

[figure not shown]
#### 9.2.1.1. Study entry and Time 0

The identification of potential Time 0s for the exposure and comparator groups is illustrated in Figure 2—a schematic of 2 hypothetical individuals with diagnoses of CKD and T2D, 1 of whom initiates finerenone.

The date of an individual's first observed prescription for finerenone during the cohort entry period will be Time 0 for the exposure group (i.e., the date a patient was initially prescribed finerenone). The selection criteria (Section 9.2.1.2) for the exposed group will be evaluated on Time 0. Only the first observed finerenone initiation date per person will be considered.

The comparator group of patients with T2D and CKD untreated with finerenone will consist of all encounters during which an individual was recognised as having CKD and was eligible to be prescribed finerenone but was not. All calendar dates with an encounter with a recorded diagnosis of CKD will be considered as potential Time 0s. The selection criteria (Section 9.2.1.2) will be evaluated at every identified potential Time 0, and all Time 0s meeting the selection criteria will be included in the comparator group. Multiple comparator Time 0s per person may be eligible and selected (Figure 2), including dates for individuals who subsequently initiate finerenone (i.e., information on an individual's future prescription or dispensing for finerenone will not be used to define eligibility). Although this is difficult to confirm before conducting the analysis, the general assumption is that patients with CKD and T2D would visit a physician at least once per year. At each interaction, the physician could potentially recognise the patient as having CKD (i.e., record the diagnosis in the electronic health record [EHR]). When combining the above assumption with an estimated maximum study period of 3 years, we anticipate the number of potential Time 0s per individual in the comparator group to generally be less than 5.

T2D = type 2 diabetes.

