#### 9.3.3.1. Primary composite cardiovascular outcome

The primary composite cardiovascular outcome will evaluate the first occurrence of any of the following events during follow-up:

- An inpatient hospital diagnosis of fatal or nonfatal acute myocardial infarction [29]
- An inpatient hospitalisation with a primary diagnosis of heart failure [30]

Individuals with prior cardiovascular events are eligible for finerenone treatment; thus, those with an occurrence of these events before Time 0 may be included in the overall study cohort (before application of outcome-specific exclusion criteria). However, to ensure identification of cardiovascular outcomes that newly occur after Time 0, analysis of this composite cardiovascular outcome will be performed in an analysis set that also excludes individuals with an acute myocardial infarction diagnosis in the 365 days before Time 0. Those with a history of heart failure will be included in the analysis, and history of heart failure will be included.

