### 9.3.3.2.2. Hospitalisation for heart failure

Finerenone is indicated in the US to prevent hospitalisations for heart failure, among other events [13]. Hospitalisation for the heart failure outcome will identify the first occurrence of an inpatient hospitalisation with a primary diagnosis of heart failure [30] during follow-up. This analysis will include individuals with a history of heart failure before Time 0, and history of heart failure will be included as an adjustment variable. No outcome-specific exclusion criteria will be applied, but this outcome will be evaluated in the same analysis set as the primary composite outcome.

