This study will compare finerenone users with nonusers. While the study selection criteria are designed to ensure that all nonusers are eligible to be prescribed finerenone on all identified Time 0s, systematic differences in characteristics may be present between finerenone initiators and nonusers, resulting in unmeasured confounding (e.g., if finerenone users are generally at more advanced disease stages than nonusers, there may be a confounded estimate demonstrating an elevated outcome rate in treated individuals). This study uses a rich set of covariates, including demographic characteristics, comorbidities, and comedications, as well as proxies for healthcare-seeking behaviour and healthy lifestyle. The balance of measured characteristics will be evaluated, negative control outcomes will be evaluated to determine the potential impact of unmeasured confounding, and a sensitivity analysis will use restrictive inclusion criteria to create more similar treatment groups. However, the possibility of unmeasured confounding remains.

Comparisons of medication users with nonusers may be subject to selection bias if treated individuals must meet additional criteria (e.g., additional survival, healthcare interactions) to be included in the study beyond those of the comparator group criteria. For the comparator group in this study, all dates on which individuals had a recorded CKD diagnosis and were eligible for finerenone treatment will be included in the comparator group. This will include a large array of individuals with CKD at each timepoint their CKD was recognised and evaluated. However, if in practice, there are requirements for finerenone prescription that systematically require additional survival (e.g., a long evaluation period), selection bias may be present. This limitation also applies to analyses of the recommended titration schedule of finerenone. Individuals who do not follow the titration schedule will be censored, potentially introducing selection bias in follow-up. Inverse probability of censoring weights will be used to account for selection bias, but residual bias may remain if some key characteristics are not measured in the data.

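### Comparator Time 0s may fall inside a hospital stay, and no rule deals with a heart failure admission open at Time 0, which risks bias in favour of finerenone

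*Protocol*

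**What the plan says.** The two groups enter the cohort through different events. For users, Section 9.2.1.1 says that the "first observed prescription for finerenone during the cohort entry period will be Time 0 for the exposure group"; Section 9.3.2 extends this to the first prescription or dispensing record. For nonusers, the same section says "All calendar dates with an encounter with a recorded diagnosis of CKD will be considered as potential Time 0s", and every such date that meets the selection criteria is kept. Section 9.9 repeats the rule: "all dates on which individuals had a recorded CKD diagnosis and were eligible for finerenone treatment will be included in the comparator group". Section 9.2.1.2 contains no criterion on care setting or on being in hospital at Time 0.

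Section 9.2.1.1 also forecasts the number of records. It states that "the general assumption is that patients with CKD and T2D would visit a physician at least once per year" and, for a study period of at most 3 years, "we anticipate the number of potential Time 0s per individual in the comparator group to generally be less than 5".

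The heart failure part of the primary outcome is "An inpatient hospitalisation with a primary diagnosis of heart failure" (Section 9.3.3.1). Follow-up starts on the day after Time 0 (Section 9.2.1.3). The primary outcome is analysed in an "analysis set that also excludes individuals with an acute myocardial infarction diagnosis in the 365 days before Time 0". Section 9.3.3.2.1 gives the reason: events should be new, not ongoing care for an earlier one. For heart failure admission, Section 9.3.3.2.2 says "No outcome-specific exclusion criteria will be applied, but this outcome will be evaluated in the same analysis set as the primary composite outcome".

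**The concern.** A nonuser admitted to hospital, with chronic kidney disease (CKD) coded during the stay, meets the Time 0 rule on that date, and possibly on each coded day of the stay. Two things can follow.

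- **Carry-over.** If the stay is for heart failure and the outcome is dated by discharge or by a later claim, the stay open at Time 0 can be counted as an outcome from day 1. The protocol guards against this for AMI but not for heart failure.
- **Risk at entry.** Even if the open stay is not counted, these records belong to patients in an acute phase, with a high chance of early readmission. Unless users enter in that state equally often, the comparator risk is raised.

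Both push the estimate towards apparent benefit, on the primary outcome and on its heart failure component. They also run against the protocol's own aims. Section 9.1 says that the design lines up eligibility with the start of follow-up. Section 9.9 says that the criteria are meant to avoid untreated patients whose clinical state makes treatment unlikely and a bad outcome more likely.

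**Working it through.** **The plan's own figure.** Section 9.5 assumes a risk ratio of 0.86, comparator risks of 14.4% and 7.2%, and a 10:1 ratio. It gives 30,000 and 60,000 records for more than 80% probability that the 95% interval excludes 1. A pooled two-proportion calculation gives 83.2% and 80.2%, and 30,000/11 = 2,727 and 60,000/11 = 5,455 users, as stated. The study size is therefore not in question. It supplies the risks and the effect against which a bias can be judged.

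**Bias illustration.** Let r be the comparator risk from Section 9.5, f the share of comparator Time 0s that fall in a hospital stay, and q the probability that such a record has a counted primary event. The documents give neither f nor q, so both are assumptions. With no drug effect, no adjustment and no such records among users:

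spurious RR = r / [r(1 − f) + f·q]

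For f = 5% and q = 30%:

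- r = 7.2%: 0.072 / (0.0684 + 0.0150) = 0.072 / 0.0834 = 0.863
- r = 14.4%: 0.144 / (0.1368 + 0.0150) = 0.144 / 0.1518 = 0.949

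| f | q | RR at r = 7.2% | RR at r = 14.4% |
|---|---|---|---|
| 2% | 15% | 0.979 | 0.999 |
| 1% | 30% | 0.969 | 0.989 |
| 5% | 30% | 0.863 | 0.949 |
| 10% | 40% | 0.687 | 0.849 |
| 1% | 100% (open stay counted) | 0.886 | 0.944 |
| 5% | 100% (open stay counted) | 0.608 | 0.771 |

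The share that would by itself produce the planned 0.86 is f = r(1/0.86 − 1)/(q − r):

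- r = 7.2%: 5.1% for q = 30%, and 1.3% for q = 100%
- r = 14.4%: 15.0% for q = 30%, and 2.7% for q = 100%

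If a share g of users also enter in hospital, the numerator becomes r(1 − g) + g·q. With r = 7.2%, f = 5%, q = 30% and g = 1%, the ratio is 0.07428/0.0834 = 0.891. It returns to 1 when g = f.

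**What the weights do.** Section 9.3.4 lists heart failure history, and hospital and emergency use in the 365 days up to and including Time 0. It lists neither inpatient status at Time 0 nor the recency of a heart failure admission, so a stay in progress and one 11 months old look alike. Stabilised weights do not remove such records: at 10:1 a comparator's weight is 0.909/(1 − PS), where PS is the propensity score, so it is never below 0.909 without trimming.

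**Record count.** One visit a year over 3 years is about 3 Time 0s. A single stay with CKD coded on several days can add several more, which sits badly with the forecast of fewer than 5.

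**The case against.** A reader might infer that the primary result is biased in favour of finerenone. The documents do not support that. They give neither the share nor the risk of in-hospital Time 0s, nor the setting in which finerenone is started. The missing heart failure rule applies to both groups, so users who start soon after an admission also stay in. Section 9.9 names confounding in the opposite direction, from users with more advanced disease. The illustration matches the planned effect only for chosen inputs at the lower risk; at 14.4% the same inputs give 0.95. These points stand.

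A reader might also infer that weighting cannot deal with the problem. That too goes beyond the text. Relevant covariates are listed. Section 9.7.2 foresees changing eligibility if the propensity score distributions differ, and further covariates, trimming or weighting to the treated population if imbalance remains. A negative control analysis comes before the primary one, and Section 9.9 mentions a sensitivity analysis with tighter inclusion criteria. These measures help but do not close the gap. The remedies are contingent, Section 9.7.7 describes only the negative control, and its candidates, asthma visits and hand laceration, would not reveal carry-over of a heart failure stay.

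Third, the physician-visit wording suggests that routine visits were meant, and the unseen SAP may define an encounter or date admissions. Inclusion of hospital days is indeed inferred from an unrestricted word. But the visit wording supports a forecast, not a filter. The all-dates rule stands in the protocol twice, and an SAP that narrowed it would depart from the protocol. Whether an open stay would be counted does remain unknown.

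Finally, keeping patients with heart failure history is a deliberate and reasonable choice, and a true early readmission is a real event. Neither is disputed. The AMI window may also be given in Figure 1, which was not available.

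**Conclusion.** The point holds as a risk of bias, not as a demonstrated one. The entry rule as written admits nonusers during a hospital stay and lets one stay supply several Time 0s. The heart failure component has no counterpart to the AMI guard. The listed covariates cover this only in part.

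This mechanism favours finerenone if users enter in hospital less often than nonusers, which is plausible but not documented. Its size cannot be fixed from the documents. Over the assumed range of f from 2% to 10% and q from 15% to 40%, the spurious ratio runs from 0.98 to 0.69 at 7.2% risk and from 1.00 to 0.85 at 14.4%, before any adjustment. If open stays are counted, a share of 1% to 3% is enough to produce 0.86. The net direction of all biases together is open.

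**What to change.** - **Section 9.2.1.1:** limit comparator Time 0s to outpatient encounters and, in both groups, exclude any Time 0 that falls during an inpatient stay.
- **Section 9.3.3:** count an AMI or heart failure outcome only if the admission starts on day 1 or later. Write the AMI washout as days [-365, 0], in the style of the windows in Section 9.2.1.2, so that an AMI coded on Time 0 is clearly removed.
- **Sensitivity analyses:** exclude Time 0s within 30 days after discharge; exclude Time 0s after a recent heart failure admission; and use all encounters, as now written. The 30-day exclusion narrows the eligible population that Section 9.2.3 wants to represent, so it belongs here and not in the primary analysis.

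The cost is protocol wording and a care-setting filter. Some comparator records are lost, but Section 9.5 expects far more than are needed. A few users who started in hospital are also lost, against an expected 20,000 or more.
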